### 2.2. Definitions of Study Days

Study days will be calculated relative to the date of the first dose of study drug. The day of the first dose of study drug will be Day 1, and the day immediately before Day 1 will be Day -1. There will be no Day 0 in this study.

The following conventions will be used to calculate study day for reporting purposes:

- Study Day = evaluation date – first dose date +1 if date of measurement is on or after the first dose date.
- Study Day = evaluation date – first dose date if date of measurement is prior to the first dose date.

Unless otherwise specified, study days for participants initially randomized into an active MORF-057 treatment group will be calculated relative to the date of the first dose in the Induction Period. However, for participants initially randomized into the placebo group, study days will be calculated separately for the Induction Period, the Maintenance and Extension Treatment Periods. During the Induction Period, study days for this group will be calculated relative to the first dose date of the induction treatment. During the Maintenance and Extension Periods, study days for this group will be calculated relative to the first dose date of the maintenance treatment recorded on the Study Period Transition eCRF page. For participants in this group who have discontinued the study before entering the Maintenance Period, no study days will be calculated for the Maintenance and Extension Period.

## 2.3. Mapping Rules for Early Treatment Termination and Unscheduled Visits

If a participant discontinued from study drug prematurely, they will be encouraged to complete the end of treatment (EOT) Visit at the time of study drug discontinuation and the Safety Follow-up Visit (visit to occur 4 weeks after the last dose of study drug is received). In the analyses, the efficacy and safety parameters measured at the EOT Visit will be re-allocated according to the following rules:

- If the assessment date for a given parameter at the EOT Visit is closer to the previous scheduled study visit date (the scheduled study visits are the general visits specified in the Schedule of Activities in Section 1.2 of the study protocol) and this parameter is scheduled to be measured at that visit but there is no measurement, the EOT Visit for this parameter will be re-allocated to the previous scheduled study visit. This re-allocation will not apply if the EOT visit falls within the Maintenance Period and the previously scheduled study visit occurs during the Induction Period.
- If the assessment date for a given parameter at the EOT Visit is closer to the next scheduled study visit date and this parameter is scheduled to be measured at that visit but there is no measurement, the EOT Visit for this parameter will be re-allocated to the next scheduled study visit. This re-allocation will not apply if the EOT visit falls within the Induction Period and the next scheduled study visit occurs during the Maintenance Period.
- Otherwise, the EOT visit will remain unassigned to a nominal visit.

The above re-allocation of the EOT Visit will be performed for each efficacy and safety parameter based on its individual scheduled visits in the protocol. Please see Section 1.2 of the study protocol for the scheduled visits for each parameter to be measured.

In addition, any clinical laboratory parameters, vital signs, and ECG measured at the unscheduled visits will be re-allocated according to the same rules above.

## 2.4. Missing Data

Unless otherwise specified, there will be no substitutions made to accommodate missing data points, and the observed cases, without imputation, will be used for the analyses.

### 2.4.1. Handing of Partial Dates on UC Diagnosis Dates

For partial UC diagnosis dates, the following imputation methods will be applied:

- If month and year are present but day is missing, then the day will be set to the first day of the month.

- If year is present but not month and day, month and day will be set to January 1st.

#### **2.4.2. Handling of Partial Dates for Adverse Events or Concomitant Medications**

When determining the treatment emergent adverse events (TEAEs) or concomitant medications, partial dates will be handled as follows:

##### **Start Dates**

- If the year is unknown, then the date will not be imputed and will be assigned a missing value.
- If the month is unknown, then:
  - If the year matches the first dose date year, then impute the month and day of the first dose date.
  - Otherwise, assign ‘January.’
- If the day is unknown, then:
  - If the month and year match the first dose date month and year, then impute the day of the first dose date.
  - Otherwise, assign the first day of the month.

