##### **Stop Dates**

- If the year is unknown, then the date will not be imputed and will be assigned a missing value.
- If the month is unknown, then assign ‘December.’
- If the day is unknown, then assign the last day of the month.
- If the imputed date is after end of study date, then end of study date will be used.

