#### 4.5. Prior and Concomitant Medications

All medications will be coded using Anatomical Therapeutic Chemical (ATC) classification based on the most recent version of the World Health Organization Drug Dictionary (WHO-DD) available at time of database lock.

Prior medications are defined as any medications that start prior to the first dose of study drug (MORF-057 or placebo).

A concomitant medication is defined as any medication taken between the first dose date of study drug and the last dose date of study drug (inclusive). Medications initiated before the first dose date and still ongoing on the first dose date or missing stopping date will be considered as both prior and concomitant medications.

The number and percentage of participants who have taken prior medications for UC disease, general prior medications excluding medications for UC disease or concomitant medications will be summarized by ATC level 4 and preferred term for each randomized treatment group and overall for FAS. A participant will be counted only once for the medications taken more than once.

Concomitant medications will be summarized for the Induction Period, the 52-week Treatment Period, and the 104-week Total Treatment Period.

The summary of concomitant medications for the Induction Period will only include concomitant medications that occurred on or before the last dose of induction period treatment.

The summary of concomitant medications for the 52-week Treatment Period will include the concomitant medications taken during the 52-week Treatment Period for participants initially randomized into an active MORF-057 treatment group and include only the concomitant medications taken during the Maintenance Period for participants initially randomized into the placebo group and subsequent switched to the MORF-057 treatment during the Maintenance Period.

The summary of concomitant medications for the 104-week Total Treatment Period will include the concomitant medications taken during the 104-week Total Treatment Period for participants initially randomized into an active MORF-057 treatment group, and include only the concomitant medications taken during the Maintenance and Extension Periods for participants initially randomized into the placebo group and subsequent switched to the MORF-057 treatment during the Maintenance and Extension Periods.

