#### 4.9.1. Adverse Events

Adverse events (AEs) will be coded using the Medical Dictionary for Regulatory Activities (MedDRA) dictionary (effective version at the time of database lock) by System Organ Class (SOC) and Preferred Term (PT). Grading of AE will be performed in accordance with CTCAE Version 5.0.

A treatment-emergent AE (TEAE) is defined as an AE that occurs during the period from the administration of the first dose of study drug up to 7 days after the last dose of study drug.

AEs will be classified as related or not related to the study drug by Investigator. If the relationship of an AE is missing/unknown, the AE will be considered study drug related.

The following summary tables will be presented:

- Overall Summary of TEAEs.
  - TEAE
  - Serious TEAE
  - TEAE with grade 3 or worse
  - Treatment-related TEAE
  - Treatment-related serious TEAE
  - TEAE leading to death
  - TEAE leading to permanent treatment discontinuation
- TEAEs by system organ class (SOC) and preferred term (PT).
- TEAEs by SOC, PT, and maximum Severity.
- TEAEs by SOC, PT, and relationship to Study Drug.

- Serious TEAE by SOC and PT
- Serious TEAEs by SOC, PT, and maximum Severity
- Serious TEAEs by SOC, PT, and Relationship to Study Drug
- Non-serious TEAEs (PTs with an incidence >5%) by SOC and PT
- TEAEs leading to permanent treatment discontinuation by SOC and PT

If more than one event occurred with the same PT or SOC for the same participant, the participant will be counted only once for that term.

The TEAE summaries for the 12-week Induction Period will include all TEAEs that occurs before the day of the first maintenance treatment for participants who have continued to the Maintenance Period, and all TEAEs for participants who have discontinued the study treatment before entering the Maintenance Period. If both the last induction treatment dose and the first maintenance treatment dose occur on the same day, any TEAEs reported on that day will be considered for the Maintenance Period and not included in the Induction Period Analysis, unless there is evidence to confirm that the TEAE occurred before the administration of the maintenance treatment.

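### The partial start-date rule ignores a known stop date, so an adverse event that ended before dosing can be counted as treatment-emergent

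*SAP*

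**What the plan says.** SAP Section 2.4.2 states the purpose of its rules: "When determining the treatment emergent adverse events (TEAEs) or concomitant medications, partial dates will be handled as follows". Under Start Dates, two branches move a partial start to the first-dose date:

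- Month unknown: "If the year matches the first dose date year, then impute the month and day of the first dose date".
- Day unknown: "If the month and year match the first dose date month and year, then impute the day of the first dose date".

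If the known parts do not match the first dose, the start goes to January or to the first of the month. If the year is unknown, the date stays missing.

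Under Stop Dates, the only cross-check is a cap: "If the imputed date is after end of study date, then end of study date will be used". Nothing in the section requires an imputed start to fall on or before the stop.

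The definitions that use these dates stand elsewhere. Section 4.9.1 gives the TEAE definition: "an AE that occurs during the period from the administration of the first dose of study drug up to 7 days after the last dose". Section 4.5 treats a medication as prior if it starts before the first dose, and as concomitant if it is "any medication taken between the first dose date of study drug and the last dose date of study drug (inclusive"). Section 4.5 brings in the stop date only for medications begun before the first dose.

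**The concern.** Moving an ambiguous start to the first dose is a sensible cautious default when nobody can tell whether the event began before or after dosing. It stops being cautious when the record already answers the question. An event with a stop date before the first dose cannot have begun on treatment, yet the two matching branches give it an onset on the first-dose day. The record then has a start later than its stop, and an onset-based derivation counts it as treatment-emergent.

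At stake are the TEAE summaries, which report the safety endpoint, and possibly the medication tables. The SAP already accepts the underlying principle at the induction/maintenance boundary. Sections 1.5.1 and 4.9.1 let evidence that an event preceded the maintenance dose override the default allocation for same-day events. The first-dose boundary has no matching exception.

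**Working it through.** The SAP states no figure on this point, so the check is to apply the rules as written to test records.

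**Inputs.** The start and stop rules are from Section 2.4.2, the TEAE definition from Section 4.9.1 and the medication definitions from Section 4.5. Assumed for illustration: first dose 15 May 2023, last dose 12 May 2024.

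**Rules as written.**

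| Recorded start | Recorded stop | Imputed start | Start minus stop | TEAE by onset | Prior medication |
|---|---|---|---|---|---|
| month unknown, 2023 | 20 Apr 2023 | 15 May 2023 | +25 days | yes | no |
| day unknown, May 2023 | 10 May 2023 | 15 May 2023 | +5 days | yes | no |
| day unknown, Apr 2023 | 20 Apr 2023 | 1 Apr 2023 | -19 days | no | yes |
| month unknown, 2022 | 20 Apr 2023 | 1 Jan 2022 | before stop | no | yes |
| month unknown, 2023 | 20 Jun 2023 | 15 May 2023 | before stop | yes | no |

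Rows 1 and 2 are wrong, because both records ended before dosing. Rows 3 and 4 fall into the non-matching branches and come out correctly. In row 5 the first-dose default does what it should. The fault is therefore confined to the two matching branches combined with a stop before the first dose.

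For medications in rows 1 and 2 there are two readings. Judged on the imputed start alone, the drug is concomitant. If the program also requires the stop to be on or after the first dose, the drug is neither prior nor concomitant. Neither result is right for a drug that ended before dosing.

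**With a stop-date condition added.** Row 1 becomes 1 Jan 2023 and row 2 becomes 1 May 2023. Both are then not treatment-emergent and count as prior only. Rows 3 to 5 do not change.

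**How often the branches fire.** This can be worked out only for records that already have a partial start and a pre-dose stop, and only under assumed timing. Take the first dose as uniform over a 365-day year.

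- Adverse events starting 2 to 42 days before dosing (Section 1.2 allows up to 6 weeks of screening), all 41 gaps equally likely. Start in the same month as dosing: sum over months and gaps of max(0, month length - gap) / (365 × 41) = 5,020 / 14,965 = 33.5%. Start in the same year: 1 - 22/365 = 94.0%, where 22 days is the mean gap.
- Drugs with a year-only start, stopped 1 to G days before dosing after 0 to G days of use: mean of max(0, 365 - gap - duration) / 365. This gives 83% for G = 60, 51% for G = 180 and 17% for G = 365.

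These are conditional rates and they move widely with the assumptions. They say nothing about how many such records the trial holds.

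**The case against.** The strongest reply is that the consequence is small and one-sided. The rule is the same in every arm, and any error adds TEAEs rather than hiding them. Section 4.9.1 also provides a listing of all adverse events, where a start after a stop would be visible. A screening event with an unknown start month but a stop known to precede dosing is an unusual record. All of this stands as a limit on size. It does not make the rule right, since the tables would still count events that the data show were over before dosing.

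The second reply concerns medications, and it largely stands. Section 2.4.2 confines the imputation to treatment-emergent and concomitant status and does not say that it decides prior status. A drug with a recorded stop before dosing was also not taken during treatment, whatever start is imputed. A reader might infer that the concomitant tables must gain such drugs and the prior tables must lose them. The text supports this only as a possible result, depending on programming.

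Two further inferences are tempting and not supported:

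- That the baseline corticosteroid and immunomodulator subgroups in Section 4.8.4 are affected. Section 4.3 settles both through code searches plus blinded manual review, completed before unblinding, not through an imputed date flag. Corticosteroid-free remission in Table 2 depends on use on Day 1. An ongoing steroid whose start is imputed to the first-dose date still meets that condition.
- That an adverse event with an unknown start year is excluded from the TEAEs. Section 2.4.2 leaves the date missing, and no section says how such an event is then classified.

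**Conclusion.** The point holds for adverse events. As written, Section 2.4.2 gives an onset on the first-dose date to any event whose partial start matches the first dose in the way described, even if its recorded stop is earlier. Section 4.9.1, applied to that onset, makes the event treatment-emergent. This assumes that TEAE status is derived from the imputed onset, and that events ending before the first dose are recorded as adverse events at all.

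For medications the point is conditional. If the imputed start is used, a drug stopped before dosing loses prior status and ends as concomitant or as neither.

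The number of affected records cannot be derived from the SAP and is probably small. The primary and secondary efficacy tests do not use these dates. The point should be fixed because a stated rule gives a demonstrably wrong answer and the repair is trivial, not because it threatens the trial's conclusions.

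**What to change.** In both matching branches of Section 2.4.2 (Start Dates), add a condition:

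- If the stop date is missing, or is on or after the first dose, impute the first-dose date as now.
- Otherwise impute the earliest date consistent with the known parts of the start date (1 January for a known year, the first of the month for a known month and year), never later than the stop date. Classify the record as pre-treatment (adverse event) or prior (medication).

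A partial stop can be completed first with the existing Stop Dates rules. These give the latest possible date, so the condition redirects only records that certainly ended before dosing. It would also help to state whether the imputed start decides prior status under Section 4.5.

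The cost is two or three sentences in the SAP and one extra condition in the date-imputation program. No new data are needed, and records with a missing stop or a stop on or after the first dose are handled as before.

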Participants who do not enroll into the Maintenance Extension must complete the final SFU Period for the main part of the study, including the Week 56 Visit (4 weeks after receiving the last dose of MORF-057), for a maximum time on study of 62 weeks. Participants who choose to continue in the Maintenance Extension will not complete the SFU Period for the main part of the study; instead, they

Morphic Therapeutic, Inc.  
Study Number: MORF-057-202

Statistical Analysis Plan  
Version 1.0, 16SEP2024

will directly enter the Maintenance Extension and complete a separate SFU Period, including the Week 108 Visit (4 weeks after receiving the last dose of MORF-057), for a maximum time on-study of 114 weeks.

An independent Data and Safety Monitoring Board (DSMB) will review participant safety data and monitor scientific integrity throughout the study. Details related to the DSMB will be clearly delineated in the DSMB Charter.

[figure not shown]
Enrolled participants will be randomized to a treatment group to receive active MORF-057 or placebo. Participants initially randomized into an active MORF-057 treatment group will receive an active treatment (according to study period and group assignment) for the full 52-week Treatment Period. Participants initially randomized into the placebo group will be switched to an active MORF-057 regimen (200 mg once a day – evening [Q.D.E]) after they complete the Induction Period and the Week 12 assessments. After participants complete the full 52-week Treatment Period, they will have the option to enter an additional 52-week Maintenance Extension Period. All participants who choose to continue in the Maintenance Extension will continue receiving the same MORF-057 regimen they had during the Maintenance Period for up to an additional 52 weeks. The dosing regimens for the 4 treatment groups during the study are shown below.

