#### **1.5. Planned Analysis**

The Treatment Period (i.e., 52 weeks) in the main part of the study includes the 12-week Induction Period and the 40-week Maintenance Period, see Section 1.2. The Induction Period includes the placebo group as a comparator, while all the participants will receive an active MORF-057 treatment during the Maintenance Period. For the purpose of statistical analyses, the Induction Period and the Maintenance

Period will be treated as 2 independent parts. There will be 2 analyses planned for the main part of the study: one for the 12-week Induction Period (i.e., the period for the primary efficacy endpoint) and one for the 52-week Treatment Period (i.e., the 12-week Induction Period plus the 40-week Maintenance Period).

Additionally, at the end of the optional Extension Period, another analysis will be performed for the 104-week Total Treatment Period, which includes the main part of the study and the 52-week Maintenance extension period.

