In the TEAE summaries for the 52-week Treatment Period and the 104-week Total Treatment Period, for participants randomized to the placebo group during the induction period who have subsequently received MORF-057 200 mg Q.D.-E during the Maintenance Period, only the TEAEs that occurs on or after the first day of maintenance treatment dose will be included and presented in the treatment group denoted by 200 mg Q.D.-E. If both the last induction treatment dose and the first maintenance treatment dose occur on the same day, any TEAEs reported on that day will be included in the summaries for this group, unless there is evidence to confirm that the TEAE occurred before the administration of the maintenance treatment. If there are any participants who were randomized to placebo group during the Induction Period and continued to the Maintenance Period but having the actual maintenance treatment different from MORF-057 200 mg Q.D.-E by mistakes, they will not be included in the summaries but presented separately as appropriate.

In addition, the TEAE for the 104-week Total Treatment Period will be summarized based on both the safety population, and the subset of the Safety Population who have continued to the Extension Period.

The following line listings will be provided:

- Listing of all AEs
- Listing of serious TEAE
- Listing of TEAEs leading to withdrawal of study treatment
- Listing of all deaths

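### Partial adverse-event start dates are imputed from the first dose only, although events are assigned to Induction or Maintenance by the first maintenance dose, so some post-switch events land in the wrong period (minor)

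*SAP*

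**What the plan says.** SAP section 2.4.2 sets one convention for every participant: "When determining the treatment emergent adverse events (TEAEs) or concomitant medications, partial dates will be handled as follows". Its start-date rules use a single reference date.

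- Month unknown: "If the year matches the first dose date year, then impute the month and day of the first dose date". In any other year, January is assigned.
- Day unknown: "If the month and year match the first dose date month and year, then impute the day of the first dose date". In any other month: "Otherwise, assign the first day of the month".

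Neither the first maintenance dose, nor the stop date, nor the visit of first report enters these rules.

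For Group 4 the first dose is placebo. Section 1.2 says that after Week 12 these participants "will be switched to an active MORF-057 regimen". Section 4.9.1 then classifies events by the first maintenance dose. For participants who continue, the Induction summaries "will include all TEAEs that occurs before the day of the first maintenance treatment". In the 52- and 104-week summaries for Group 4, "only the TEAEs that occurs on or after the first day of maintenance treatment dose will be included", shown as 200 mg Q.D.-E. Groups 1 to 3 are summarized cumulatively in those two analyses.

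**The concern.** The rule that creates the date does not know the boundary that later classifies it. An event that began on MORF-057 in a Group 4 participant can be given a start date in the placebo period. It is then missing from the 200 mg Q.D.-E column and from the pooled MORF-057 column of the long-term safety tables, and it appears under placebo in the Induction table. Group 4 is the only source of data on 200 mg Q.D.-E, so nothing else makes up for an undercount there. Elsewhere the SAP does restart the clock for this group: safety baseline (2.1.1), study day (2.2) and exposure (4.6.1.2) all name the first maintenance dose. Section 2.4.2 has no matching branch.

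**Working it through.** The SAP states no figure here, so there is none to reproduce. The check applies the section 2.4.2 rules literally.

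**Inputs.** Section 1.5 gives the "12-week Induction Period and the 40-week Maintenance Period, see Section 1.2", that is 84 and 280 days. Section 4.9.1 extends the TEAE window 7 days past the last dose, which gives 280 + 7 = 287 post-switch days. Assumptions: switch dates spread evenly over the calendar, event days uniform over the 287 days, and January read as 1 January.

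**Examples (invented dates).**
- First dose 10 March 2023, switch 84 days later on 2 June, true onset 7 June. Day unknown gives 1 June; month unknown gives 10 March. Both precede the switch.
- First dose 10 November 2023, switch 2 February 2024, true onset 20 August 2024. Month unknown gives 1 January 2024, before the switch. Day unknown gives 1 August 2024, which is correctly in Maintenance.

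**Which branch is at fault.** The branch that matches the first-dose month is harmless. With the switch 77, 84 or 91 days after first dose, the switch never falls in the first-dose month (0 cases). The errors come from three lines: the 1st of the month, the first-dose-year rule, and January.

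**Day unknown.** Suppose the switch is on day s of a month with m days. That month then holds m − s + 1 post-switch days, and all of them are imputed to the 1st. This is before the switch unless s = 1.
- Share of switch-month events misplaced: [m(m − 1)/2] / [m(m + 1)/2] = (m − 1)/(m + 1). For m = 30, 29/31 = 93.5%. Enumeration over four calendar years gives 93.6%.
- Share of all day-unknown post-switch events misplaced: [(m − 1)/2] / 287. For m = 30, 14.5/287 = 5.1%. Enumeration gives 5.1%.

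**Month unknown.** Every post-switch event in the calendar year of the switch is dated to the first dose or to 1 January, so it falls before the switch unless the switch is itself on 1 January. With the switch on day d of a 365-day year, min(287, 366 − d) post-switch days fall in that year.
- Days 2 to 79: 78 × 287 = 22,386.
- Days 80 to 365: 286 + 285 + … + 1 = 41,041.
- Share: (22,386 + 41,041) / (365 × 287) = 63,427 / 104,755 = 60.5%. Enumeration over four calendar years, including a leap year, gives 60.6%.

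The enumerated results are the same for a switch at day 77, 84 or 91.

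**Illustration in events (assumed).** Take all 70 Group 4 participants entering Maintenance with 3 events each, 210 events, of which 1% to 3% have partial dates: 2.1 to 6.3 events. If all are day-unknown, 0.051 × 2.1 to 0.051 × 6.3 = 0.1 to 0.3 events move. If all are month-unknown, 0.606 × 2.1 to 0.606 × 6.3 = 1.3 to 3.8 events move.

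**The case against.** Four arguments weigh on the other side.

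- **The first dose date could be read as the first maintenance dose for Group 4.** Section 2.4.2 does not say so, and sections 2.2 and 4.6 name the maintenance dose explicitly when they mean it. This does not rescue the rule.
- **Very few events are touched.** This stands. Day-unknown events in months after the switch month are allocated correctly, so a reader should not infer that partial-date events after the switch are lost in general. Only the month-unknown case is badly affected.
- **The rule is the same in every arm.** This also stands. A reader might infer that the errors run one way and load the placebo comparator. But section 4.9.1 splits every continuing participant at the first maintenance dose, so Maintenance events in Groups 1 to 3 also move into the Induction table, the only one with a placebo column. The shift need not be equal across arms, but a one-sided bias is not shown. The cumulative 52- and 104-week counts in Groups 1 to 3 are unaffected.
- **The same-day rule already covers ambiguity.** It does not help, because the imputed dates fall before the switch day. Nor does it make section 2.4.2 contradict the plan's own principle, as a reader might infer. The same-day rule covers events on a known day when both doses fall on it and states no policy for partial dates. This is a gap, not a contradiction.

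**Conclusion.** The point holds, and it is minor. Followed as written, section 2.4.2 dates before the switch about 94% of post-switch events with unknown day in the switch month (about 5% of all post-switch events with unknown day) and about 61% of post-switch events with unknown month. The lasting harm is an undercount in the 200 mg Q.D.-E and pooled MORF-057 columns of the descriptive 52- and 104-week tables. In addition, Maintenance events are misdated into the Induction table in all four arms. The percentages rest on uniform event and switch dates and apply only to events with a partial date. The SAP does not say how many there will be, so the effect on the counts is unknown and probably a few events.

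**What to change.** Add one rule to section 2.4.2 for all arms.

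1. When the known parts of a start date fit both Induction and Maintenance, assign the period from a known stop date or from the visit or eCRF record at which the event was first reported.
2. If that points to Induction, keep the current imputed date. If it points to Maintenance, or the period is still unresolved, use the later of the current imputed date and the first maintenance dose date.
3. No imputed start may fall after a known stop date.

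Apply the same period logic to concomitant medications, which section 4.5 also splits at the first maintenance dose. The effect there is smaller: under section 4.5 a drug dated too early but still taken on the first Maintenance day generally counts in Maintenance as well, so the error mainly adds entries to Induction.

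The rule should not be limited to Group 4, because that would treat the arms differently in the randomized Induction table. Step 1 is also essential. Simply re-anchoring to the first maintenance dose would remove the misplacement of post-switch events (5.1% and 60.6% both fall to 0%), but it would move 16% to 19% of day-unknown and 87% to 89% of month-unknown true Induction events into Maintenance.

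The cost is a few sentences of SAP text and minor programming before database lock. Some unresolved true Induction events in every arm will still be attributed to Maintenance; for Group 4 that means attribution to active drug, the conservative direction.
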